Serious hemorrhagic AEs have been reported from clinical studies investigating ramucirumab. Hemorrhagic complications are associated with some malignancies (that is, variceal bleeding from portal hypertension in hepatocellular carcinoma, lower GI hemorrhage from bowel metastases in ovarian carcinoma), although the rate of these complications varies considerably. As detailed in the ramucirumab IB, the incidences of hemorrhagic events to date, significant background incidence of bleeding in some malignancies, and use of concomitant antiplatelet therapy in some of the reported cases preclude any definitive association between bleeding and ramucirumab, although ongoing surveillance and identification (and exclusion) of patients with high bleeding risk remain essential and are detailed in the inclusion/exclusion criteria.

6.9.1.2.1.5. Gastrointestinal Perforation

Patients with unresected (or recurrent) primary tumors or mesenteric or peritoneal disease who participate in this clinical study may be at increased risk for GI perforation due to the nature of the disease (metastatic gastric-GEJ cancer).

An infrequent incidence of GI perforations has been associated with some antiangiogenic therapeutic agents, most specifically in the context of colorectal cancer (treated with combination regimens, including anti-VEGF antibodies and cytotoxic chemotherapy) and in advanced ovarian cancer. These events may be associated with extensive abdominal/peritoneal disease burden. Gastrointestinal perforation has been reported from clinical studies investigating ramucirumab. The incidences of these events to date and presence of significant comorbidities and risk factors preclude any definitive association with ramucirumab, although ongoing surveillance remains essential. More information about GI perforation may be found in the IB.

6.9.1.2.1.6. Reversible Posterior Leukoencephalopathy Syndrome

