8.2.1. Adverse Events

Lack of drug effect is not an AE in clinical trials, because the purpose of the clinical trial is to establish drug effect.

Any clinically significant findings from electrocardiograms (ECGs), labs, vital sign measurements, or other procedures that result in a diagnosis should be reported to Lilly or its designee.

After the informed consent form (ICF) is signed, study site personnel will record the occurrence and nature of each patient's preexisting conditions, including clinically significant signs and symptoms of the disease under treatment in the study. Site personnel will record the occurrence and nature of any AEs and any change in the preexisting condition(s). Progression of the cancer under study is not considered an adverse event unless it is considered to be drug-related by the investigator. All AEs related to protocol procedures are reported to Lilly or its designee.

In addition, all AEs occurring after the patient receives the first dose of IP must be reported to Lilly or its designee via CRF.

Investigators should report to Lilly or its designee their assessment of the potential relatedness of each AE to protocol procedure or IP via CRF.

The investigator decides whether he or she interprets the observed AEs as reasonably possibly related to disease, to the study regimen, study procedure, or other concomitant treatment or pathologies. To assess the relationship of the AE to the IP, the following is defined:

Reasonably Possibly Related: Reasonable possibility that there is a cause and effect relationship between the IP, study device, and/or study procedure and the AE.

The investigator answers yes/no when making this assessment.

Patients will be evaluated for AEs at each visit and will be instructed to call their physician to report any AEs between visits.

NCI-CTCAE v 4.0 will serve as the reference document for choosing appropriate terminology for, and grading the severity of, all AEs and other symptoms. For AEs without matching terminology within the NCI-CTCAE v 4.0 criteria, the investigator will be responsible for selecting the appropriate system organ class and assessing severity grade based on the intensity of the event.

In addition to collecting the AE verbatim and the CTCAE severity grade, AE verbatim text will also be mapped by Lilly or its designee to corresponding terminology within the Medical Dictionary for Regulatory Activities (MedDRA) dictionary.

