Serious adverse event collection begins after the patient has signed informed consent and has received IP and ends 90 days following cessation of treatment, or 30 days following cessation of treatment if the patient initiates new anticancer therapy, whichever is earlier. If a patient experiences an SAE after signing informed consent, but prior to receiving IPs, the event will not be reported as serious unless the investigator feels the event may have been caused by a protocol procedure.

Study site personnel must alert Lilly or its designee of any **serious** adverse event (SAE) within 24 hours of investigator awareness of the event via a Sponsor-approved method. If study site

personnel contact Lilly or its designee by telephone regarding an SAE, study site personnel must also immediately provide official notification on study-specific SAE forms.

This 24-hour notification requirement refers to the initial SAE information and all follow-up SAE information.

Planned surgeries should not be reported as SAEs unless the underlying medical condition has worsened during the course of the study.

Planned hospitalizations or procedures for preexisting conditions that are already recorded in the patient's medical history at the time of study enrollment should not be considered SAEs.

Serious adverse events due to disease progression, including death, should not be reported unless the investigator deems them to be possibly related to the IPs.

The investigator does not need to actively monitor patients for AEs once the trial has ended, unless provided otherwise in the protocol; however, if an investigator becomes aware of an SAE occurring after the patient's participation in the trial has ended, and the investigator believes that the SAE is related to a protocol procedure or IPs, the investigator should report the SAE to the Sponsor, and the SAE will be entered in the Lilly Safety System.

Information on SAEs expected in the study population independent of drug exposure and that will be assessed by the Sponsor in aggregate periodically during the course of the trial may be found in the pembrolizumab and ramucirumab IBs.

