Vital signs	X			X	X			For the first 2 ramucirumab infusions, measure blood pressure and pulse as follows: (i) within 15 minutes prior; (ii) after infusion completion; and (iii) at the end of the 1-hr post-infusion observation period. Measure blood pressure and pulse prior to each subsequent ramucirumab infusion. Measure other vital signs as clinically indicated.
AE collection; CTCAE grading	X							During short-term follow-up, all AEs/SAEs will be collected. At the 90-day long-term follow-up visit, all SAEs will be collected. Thereafter, during long-term follow-up, only SAEs that are related to study regimen or protocol procedures will be collected.

	Study Period						Notes
	Baseline (within 28 days prior to enrollment)			Treatment (21-day cycles)		Postdiscontinuation Follow-Up	
Procedure	≤28 days	≤21 days	≤7 days	Day 1	Day 8	Short-Term Follow-Up Visit (30 ±7 days)	Long-Term Follow-Up Visit (every 90 ±7 days)
Laboratory Assessment							
Hematology	X			X		X	Local only. Within 3 days prior to Day 1 of each cycle.
Chemistry	X			X		X	Local and central: Local chemistry laboratory testing will be used to determine patient eligibility and decisions for treatment. Central chemistry laboratory testing will be used for subsequent scheduled analyses. Within 3 days prior to Day 1 of each cycle.
Urinalysis	X			X		X	Local only. Within 3 days prior to Day 1 of each cycle. 24-hr urine protein analysis if urine protein is ≥2+ at baseline, >2+ during study treatment.
T3, free T4, TSH	X			X		X	Central and local as needed. At baseline, within 3 days prior to Day 1 of Cycle 3, Day 1 of Cycle 6, and every 2 cycles thereafter; and more frequently if clinically indicated.
Coagulation	X			X		X	Local only. Within 3 days prior to Day 1 of every odd-numbered cycle.
Pregnancy test			X			X	Local only. Required for women of child-bearing potential. If required per local regulations and/or institutional guidelines, testing can occur at other times during the study treatment period.

	Study Period						Notes
	Baseline (within 28 days prior to enrollment)		Treatment (21-day cycles)		Postdiscontinuation Follow-Up		
Procedure	≤28 days	≤21 days	≤7 days	Day 1	Day 8	Short-Term Follow-Up Visit (30 ±7 days)	Long-Term Follow-Up Visit (every 90 ±7 days)
Efficacy Assessment							

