5.3.7.1. Treatment-Emergent Adverse Events

Treatment-emergent adverse events will be summarized by decreasing frequency of SOC by PT and by CTCAE grade regardless of causality and related to any study drug separately. Note, “by CTCAE grade” refers to the categories of all grade, Grade 3-4, and Grade 3-5. Consolidated TEAEs will also be summarized.

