5.3.8. Deaths, Serious Adverse Events, and Other Significant Adverse Events

Reasons for deaths will be summarized separately for 1) all deaths, 2) deaths up to 30 days after the last infusion of study treatment, and 3) deaths after 30 days of last infusion of study drug. Reasons of deaths will also be listed.

Serious adverse events (SAEs) will be summarized by PT and repeated for events deemed by the investigator to be possibly related to study medication, with consolidated summary performed if needed. SAEs will be summarized both up to 30 and 90 days after end of therapy. A listing of SAEs will be produced.

In addition, the following analyses will be performed:

- AESIs for ramucirumab by PT
- AESIs for ramucirumab by PT related to study drug
- ECIs for pembrolizumab by PT
- ECIs for pembrolizumab by PT related to study drug
- Listing of AESIs, sorted in the order of phase, cohort, AESI category, PT, and patient identification
- Listing of AEs with outcome of death or discontinuation

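### Protocol 8.2.1.2 exempts SAEs ascribed to progression unless possibly related, which conflicts with Table JVDF.7 and can leave the SAE table incomplete, with no AE backstop between the 30-day and 90-day visits

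*Protocol*

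**What the plan says.** Protocol 8.2.1.2, after defining an SAE and describing the 24-hour notification, states: "Serious adverse events due to disease progression, including death, should not be reported unless the investigator deems them to be possibly related" to the study drugs.

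Three other places in the protocol set a different or narrower rule:

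- **Table JVDF.7 (Section 8.2)** lists all SAEs for the collection database during study treatment, the 30-day follow-up and the period through the 90-day visit. Only after that visit does it restrict collection to SAEs related to a procedure or study drug.
- **Attachment 1, Time and Events Table**, AE collection row: "During short-term follow-up, all AEs/SAEs will be collected. At the 90-day long-term follow-up visit, all SAEs will be collected".
- **Section 8.2.1** excludes progression but not its complications: "Progression of the cancer under study is not considered an adverse event unless it is considered to be drug-related by the investigator". It adds that "all AEs occurring after the patient receives the first dose of IP must be reported to Lilly or its designee via CRF", with a relatedness answer for each.

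On the analysis side, SAP 5.3.8 says: "Serious adverse events (SAEs) will be summarized by PT and repeated for events deemed by the investigator to be possibly related to study medication". It summarizes SAEs to both 30 and 90 days after end of therapy and summarizes all deaths separately. SAP 5.3.7.1 tabulates TEAEs "regardless of causality and related to any study drug separately". SAP 5.2.1.3 runs the TEAE window to 90 days after the last dose. It also defines each ramucirumab AESI by preferred terms, with no condition on seriousness or relatedness.

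**The concern.** SAEs are a named endpoint of the primary safety objective (Protocol Section 3). Tabulating SAEs and then repeating the table for possibly related ones makes sense only if the first table does not depend on attribution. Under 8.2.1.2, an SAE ascribed to progression enters that first table only if the investigator also judges it possibly related.

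The exemption covers any serious clinical event given that cause, not just the term for progression. The events most exposed are those that both the tumor and the drugs can produce. For hemorrhage, Protocol 6.9.1.2.1.4 cites "significant background incidence of bleeding in some malignancies" as one reason why a definite link to ramucirumab cannot be drawn, and it calls continued surveillance essential. Section 6.9.1.2.1.5 makes a similar statement for GI perforation. For such events the SAE record should not depend on the judgment that the protocol itself calls difficult.

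Cohorts have 15 or 25 patients and there is no control arm, so one or two missing events can change what a cohort's SAE table shows. Sites also have two collection rules and no statement of which one governs.

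**Working it through.** No figure in the documents depends on this rule, so there is none to reproduce. The check is a side-by-side reading, followed by an illustration on assumed rates.

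**Step 1. What each rule collects, by period.** Take a serious, non-fatal hemorrhage that the investigator ascribes to progression and does not call possibly related.

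| Period | Table JVDF.7 / Attachment 1 | Under 8.2.1.2 | Where the event still appears under 8.2.1.2 |
|---|---|---|---|
| Study treatment | All AEs, all SAEs | Not reported as an SAE | TEAE and AESI tables, through the AE record |
| To the 30-day visit | All AEs, all SAEs | Not reported as an SAE | TEAE and AESI tables, through the AE record |
| 30-day to 90-day visit | All SAEs only | Not reported as an SAE | No table: no AE record is required |
| After the 90-day visit | Related SAEs only | Not reported as an SAE | Not applicable: the two rules agree for this event |

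The third row is the important one. The TEAE window and the longer SAE summary both extend to 90 days, but AE collection stops at the 30-day visit. The sentence in 8.2.1 on reporting all AEs gives no end date; Table JVDF.7 and Attachment 1 supply it. One limit applies: 8.2.1.2 also ends SAE collection 30 days after treatment stops if the patient starts new anticancer therapy. Under that text the row concerns patients who have not done so.

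**Step 2. How far the exemption extends.** Section 8.2.1 removes progression itself. Section 8.2.1.2 removes SAEs due to progression. The difference is every serious clinical complication assigned that cause, less those also judged possibly related.

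**Step 3. Outputs affected.** The first SAE table in SAP 5.3.8 is affected in all three periods through the 90-day visit. The TEAE and AESI tables are affected only between the 30-day and 90-day visits. The all-deaths summary is not affected.

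**Step 4. Illustration.** Let p be the true rate of such serious events and f the share both ascribed to progression and left unreported. The documents give neither, so both are assumed. The expected SAE count becomes (1 − f) times the true count, and

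P(at least one in the SAE table) = 1 − (1 − p(1 − f))^n.

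For example, with n = 25, p = 5% and f = 50%: 1 − 0.975^25 = 46.9%.

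| n | Assumed p | f = 0 | f = 25% | f = 50% | f = 75% |
|---|---|---|---|---|---|
| 25 | 2% | 39.7% | 31.5% | 22.2% | 11.8% |
| 25 | 5% | 72.3% | 61.5% | 46.9% | 27.0% |
| 25 | 10% | 92.8% | 85.8% | 72.3% | 46.9% |
| 15 | 2% | 26.1% | 20.3% | 14.0% | 7.2% |
| 15 | 5% | 53.7% | 43.6% | 31.6% | 17.2% |
| 15 | 10% | 79.4% | 68.9% | 53.7% | 31.6% |

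Over all 155 Phase 1b patients at p = 5%, the expected count falls from 155 × 0.05 = 7.75 to 3.88 at f = 50%. These figures describe the SAE table only. They show the direction of the effect and how sensitive small cohorts are to it; they are not estimates for this trial.

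**The case against.** The case for leaving the text alone has real force.

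- **The exception for possibly related events sets a low bar.** Section 8.2.1 asks only whether there is a reasonable possibility of a causal link. Bleeding, perforation and thromboembolism are listed AESIs, so sites are alert to them, and many such events would be called possibly related and reported. This stands: a reader might infer that every SAE ascribed to progression is exempt, and that is wrong.
- **The sentence may concern expedited notification only.** It follows the 24-hour text, and Table JVDF.7 distinguishes the collection database from the sponsor's safety system. Its footnote also defers to CRF guidelines that are not among the documents. The reading is possible, but the same section speaks of SAE collection, and nothing says which rule governs. That supports clarifying the text.
- **Other tables preserve most of the information.** TEAEs are tabulated regardless of causality, AESIs by preferred term, and all deaths separately. This stands up to the 30-day visit, and for deaths throughout. It fails for non-fatal events between the 30-day and 90-day visits.
- **SAP 5.3.8 does not call its first SAE table all-cause.** That is inferred from the related-only repeat. The inference is reasonable but unstated.

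A reader might also infer that open-label assessment drives attribution toward progression. The documents do not show this. Every patient receives both drugs, and knowing that could raise drug attribution as easily as lower it.

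**Conclusion.** Protocol 8.2.1.2 conflicts with Table JVDF.7 and Attachment 1 and is wider than Section 8.2.1. If sites follow it, the first SAE table and the 90-day SAE summary can omit serious clinical events that are ascribed to progression and not called possibly related. Between the 30-day and 90-day visits, such an event can be absent from the SAE, TEAE and AESI tables together.

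This is a risk, not a demonstrated loss. It would be tempting to say that the SAE tables do lose bleeding and perforation events, or that the signal for them disappears. The documents support neither: a site following Table JVDF.7 would collect them all, and up to the 30-day visit the AE record should carry them into other tables. Only the direction is certain: any omission lowers the serious-event count, and there is no comparator against which to judge the shortfall. The size cannot be derived, because neither the event rate nor the attribution share is given.

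The text should be changed, because the primary safety endpoint is involved and the correction is small.

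**What to change.** **Protocol.** Reconcile 8.2.1.2 with Table JVDF.7, Section 8.2.1 and Attachment 1. Limit the exemption to progression of the cancer itself and to death with no cause other than progression. State that every other serious clinical event from first dose through the 90-day visit is recorded in the collection database as an SAE, whatever cause is assigned. Record attribution to progression in its own CRF field. Any exemption from expedited reporting can remain, provided it is labeled as such.

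**SAP 5.3.8.** State that the first SAE table includes these events. A sensitivity row omitting those ascribed to progression is optional.

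**Cost.** The change needs one protocol sentence, one CRF field and one SAP statement. There will be some more SAE records and a slightly less favorable SAE rate. Judging that a death had no cause other than progression still rests with the investigator, but the all-deaths summary covers those cases. The amendment (b) summary shows that the study was already under way, so events handled under the present sentence would need to be queried, or the change in collection noted in the report.

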8.2.1.3. Pregnancy

Cases of pregnancy that occur during maternal or paternal exposures to IPs (ramucirumab or pembrolizumab) should be reported within 24 hours. Pregnancy outcomes of spontaneous abortion, missed abortion, benign hydatidiform mole, blighted ovum, congenital abnormality, fetal death, intrauterine death, miscarriage and stillbirth, or other disabling or life-threatening complication to the mother or newborn must be reported as AEs. Data on fetal outcome (including and breastfeeding) are collected for regulatory reporting and drug safety evaluation. The following additional measures will be taken in the case of pregnancy:

- A patient who becomes pregnant will be immediately removed from the study.
- It is the responsibility of investigators or their designees to report any pregnancy or lactation in a patient (spontaneously reported to them) that occurs during the trial or within 120 days of completing the trial or 30 days following cessation of treatment if the patient initiates new anticancer therapy, whichever is earlier.
- All patients who become pregnant must be contacted by the site at least monthly and the patient's status documented to the completion/termination of the pregnancy; the investigator will make every effort to obtain permission to follow the outcome of the pregnancy and report the condition of the fetus or newborn to the Sponsor.

8.2.1.4. Suspected Unexpected Serious Adverse Reactions

Suspected unexpected serious adverse reactions (SUSARs) are serious events that are not listed in the Development Core Safety Information in the IB and that the investigator identifies as

related to the IPs or study procedure. United States 21 CFR 312.32 and European Union Clinical Trial Directive 2001/20/EC and the associated detailed guidances or national regulatory requirements in participating countries require the reporting of SUSARs. Lilly has procedures that will be followed for the recording and expedited reporting of SUSARs that are consistent with global regulations and associated detailed guidances.

8.2.2. Other Safety Measures

8.2.2.1. Electrocardiograms

For each patient, 12-lead digital ECGs will be collected according to the Time and Events Table ([Attachment 1](#)) as single ECGs for overread. Patients must be supine for approximately 5 to 10 minutes before ECG collection and remain supine but awake during ECG collection.

Electrocardiograms may be obtained at additional times, when deemed clinically necessary. Collection of more ECGs than expected at a particular time point is allowed when needed to ensure high quality records.

Electrocardiograms will be interpreted by a qualified physician (the investigator or qualified designee) at the site as soon after the time of ECG collection as possible, and ideally while the patient is still present, to determine whether the patient meets entry criteria and for immediate patient management, should any clinically relevant findings be identified.

After enrollment, if a clinically significant increase in the QT/corrected QT interval from baseline, or other clinically significant quantitative or qualitative change from baseline, is present, the investigator will assess the patient for symptoms (for example, palpitations, near syncope, syncope) and to determine if the patient can continue in the study. The investigator or qualified designee is responsible for determining if any change in patient management is needed and must document his/her review of the ECG printed at the time of evaluation.

The investigator (or qualified designee) must document his/her review of the ECG printed at the time of evaluation. Local ECG findings at baseline and end of treatment, and any on study clinically significant abnormal findings, will be reported into the electronic CRF (eCRF) and any alert reports.

8.2.2.2. Echocardiogram or Multiple-Gated Acquisition Scan

An echocardiogram (ECHO) or multiple-gated acquisition (MUGA) scan will be performed according to the Time and Events Table ([Attachment 1](#)). Additional evaluations are not required but should be performed in the setting of cardiac symptoms, at the discretion of the investigator.

Patients will undergo baseline left ventricular ejection fraction (LVEF) determination by ECHO or MUGA scan. This evaluation may be repeated at any time during the study if clinically indicated.

